The primary substance abuse outcomes (self-reported abstinence) will be assessed throughout the study and through a six month follow-up. Additional outcomes will include use of other services (medical, legal), patient and provider satisfaction, as well as the costs of implementing the program. Each week, the counsellors will deliver a questionnaire (provided by the CHCR) which covers this range of topics to their patient participating in the trial. The data will be analyzed with a focus on feasibility (retention in both conditions, levels of substance abuse, health problems, and cost by condition).

4. SUBJECT SELECTION:

Participants will be recruited from Prince Edward Island; Lennox Island Health Centre and Abegweit Health Centre, Mount Herbert Provincial Addictions Treatment Facility Transition Unit and Methadone clinic, Holland College Student Services, University of Prince Edward Island Student Services, Charlottetown Methadone Clinic and Prince County Hospital. At RECAP in New Brunswick and Ontario Shores Mental Health Centre in Ontario.

A total of 240 Participants will be recruited during years 1-2 and an additional 440 participants will be recruited during years 3-4 ending in April 2019.

Counsellors already employed by the Centres will recruit participants who are willing to consent to a randomized trial of CBT4CBT. In order to create as representative a sample as possible, the inclusion criteria will be fairly broad, including any consenting individual who reports substance abuse in the past thirty days. Individuals who are currently suicidal, homicidal, or require immediate hospitalization will be excluded.

The participants will be patients who have reported substance abuse in the past thirty days. For the initial trial, all participating individuals will be over eighteen years of age and be approved to participate by their addictions counsellors.

Counsellors will ask individuals seeking treatment for substance abuse if they would be interested in learning about and participating in a substance abuse treatment project. If yes, participants will be introduced to the study Research Assistant who will go through the consent form(attached) with them. The Research Assistant will orally read the forms if necessary and individuals will be informed of their right to withdraw from the program should the need arise.

5. RESEARCH PLAN:

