The individuals recruited for this study will each fall into one or more subgroup of the trial (transitioning patients [inpatient to outpatient], youth [18-24 years], maintained on methadone, and indigenous individuals) and will be analyzed individually as well as collectively by compiling results from all sites. A subgroup analysis based on gender is also planned to investigate any differences in outcomes between male and female participants, these two groups, historically, can show significant differences in response to mental health and addictions treatment.

Participants will be randomized to either test or control groups. Participants in the control group will receive treatment as usual (the conventional treatment offered at that site) and will also meet with the Research Assistant during week 4 and week 8 to complete questionnaires (attached) either in hard copy or online on a tablet provided. These participants will also be contacted six months after their eight-week participation in the trial ended to complete a follow-up questionnaire.

Participants randomized to the test group will receive treatment as usual but will also be asked to spend at least thirty minutes per week using the program. CBT4CBT use by each participant will be monitored throughout the trial to ensure that this requirement is being met. They may choose to do this on location at the site or from their personal computer/tablet. The individuals in this arm of the trial will also meet with a Research Assistant once a week for eight weeks to complete questionnaires and will be contacted six months after their eight-week participation in the trial ended to complete a follow-up questionnaire. These questionnaires can be completed online. Each participant will be asked to participate in the eight-week long treatment period regardless of group (test or control). In addition to participants' treatment as usual, this will involve a

commitment of approximately 10 minutes as a weekly average from participants in the control group, and approximately 45 minutes as a weekly average from participants in the test group. Please see the consent form table outlining the time commitments in more detail.

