This trial design will mirror the designs in the trials already successfully conducted in the United States. Once an individual consents to participate, the counsellor will contact the Research Assistant who will meet with the individual and assign them a participant number generated using Randomizer.org (Geoffrey C. Urbaniak, 2015). This number will have been previously assigned to either test or control. The participant will be notified about the trial arm that they are placed into so that their participation may commence.

A Research Assistant will deliver the questionnaires to the trial participants. Questionnaires may be answered in hard copy or online in private. This removes the pressure from the participants to 'improve' in the eyes of their counsellor. Other than the addition of sections specifically relating to the CBT4CBT program, the questionnaires between groups will be identical.

As mentioned above, three previous/pilot studies in urban areas of the U.S. have been performed ([name] et al., 2008, 2009, 2014). The trial described herein will follow a very similar design.

Questionnaires, data analysis and protocols are based on those previously used by our collaborator in the US and have all been tailored to better suit Canadian populations. Based on the significant success that [name] had using these outcomes, tools and protocols we are confident in their reliability and validity.

Individuals who consent to this trial will be notified at the beginning of the trial that they have the right to remove themselves from the trial at any time. They also have the right to contact their counsellor or either co-investigator (phone numbers and emails provided on the consent form) at any time should they have questions or concerns. The counsellors also hold the ability to remove any of their patients from the trial at any time if they see fit.

6. ANALYSIS OF DATA:

Statistical analysis techniques previously used by the Co-Investigator [name] and her team will be performed on the generated data from this trial ([name] et al., 2008, 2009, 2014). These include one and two-way analysis of variance (ANOVA's) where appropriate. This will ensure a relevant analysis approach is used for the field of addictions treatment research as well as ensuring that the generated results may be compared with those previously established at other sites.

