The power calculations performed to calculate the sample size are based on three similar published trials of CBT4CBT in urban populations in the US. Primary outcome measurements of this trial will be a subset of measurements collected in these previous trials. We believe retention and follow up rates will be similar if not higher than the previous trials as PEI has a less transient community than most urban centers like Connecticut. Based on the three previous trials ([name] et al., 2008, 2009, 2014), the average drug use measurement (measured by the percent days abstinence from all drugs) in the test groups was 75% and control group 66% with a common standard deviation of 24% at the end of the eight week trial. Retention during the eight week trial was on average 77% and follow-up success was approximately 87% six months post trial. These values were used to calculate the sample size of 30 (for each group) to achieve statistical significance with an alpha of 0.5 and a power of 0.8 for subgroup analysis of the initial trials on PEI, and an alpha 0.05 and a power of 0.8 for combined analysis (i.e. combining results from

all 240 participants across the four trial settings). Power calculations to achieve statistical significance with an alpha of 0.05 and a power of 0.9 were calculated for the large-scale effectiveness trials and a sample size of 110 was found.

Primary outcomes measured include retention, changes in drug use, changes in health (e.g. medical visits, family and social satisfaction, etc.) and program implementation costs. The outcomes to be determined are identical in the four parallel trials to foster comparability across populations.

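### No baseline questionnaire is described and the arms have different questionnaire schedules, yet change in drug use is primary with no reference time

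*Combined protocol and SAP*

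**What the plan says.** Section 5 (Research Plan) gives each arm its own schedule. Control participants "will also meet with the Research Assistant during week 4 and week 8 to complete questionnaires"; test participants "will also meet with a Research Assistant once a week for eight weeks to complete questionnaires". Both arms are contacted again six months after the eight weeks.

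Between consent and allocation, section 5 describes one step. The counsellor contacts the Research Assistant, "who will meet with the individual and assign them a participant number generated using Randomizer.org", and that number is already tied to an arm. No assessment is placed there. The only earlier information on drug use is the eligibility condition in section 4 (some use in the past thirty days), which is not a scored measure.

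Section 6 (Analysis of Data) states: "Primary outcomes measured include retention, changes in drug use, changes in health". It gives no reference time for these changes. The only analysis it names is one- and two-way ANOVA, with no baseline term. Its sample size rests on percent days abstinent at the end of the eight weeks: 75% against 66%, SD 24%.

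Section 3 reads differently on two counts. It words the outcome as abstinence: "The primary substance abuse outcomes (self-reported abstinence) will be assessed throughout the study and through a six month follow-up". It also says "Each week, the counsellors will deliver a questionnaire (provided by the CHCR"), with no split by arm, whereas section 5 says "A Research Assistant will deliver the questionnaires to the trial participants".

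**The concern.** A change score needs a starting value that is measured in the same way in both arms and cannot be affected by allocation. The text supplies none. The earliest questionnaire in section 5 falls in week 1 for test and week 4 for control, and both come after the participant knows the arm. Any trend in drug use shared by the two arms would then be captured over different lengths of time, and a difference could appear with no program effect.

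Because the reference time is not stated, it could also be chosen after the data are seen. Without a baseline the analysis cannot check balance or gain precision. A baseline that was not taken before treatment starts cannot be recovered later.

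**Working it through.** **1. Schedules side by side**

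| | Before allocation | During eight weeks | Six months |
|---|---|---|---|
| Section 5, control | none described | weeks 4 and 8 | yes |
| Section 5, test | none described | weekly, 1 to 8 | yes |
| Section 3, not split by arm | none described | weekly | yes |

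The section 5 schedules share weeks 4, 8 and six months. Under section 3 both arms would also share week 1, but that is still after allocation.

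The time commitments in section 5 do not reveal a hidden baseline visit. Control: 10 min × 8 = 80 min, or 40 min for each of two visits. Test: (45 − 30) × 8 = 120 min, or 15 min for each of eight visits. Either total could include or exclude a baseline.

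**2. What an unequal starting point could do (illustration only)**

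Assume no program effect, the same linear improvement of T points of percent days abstinent over eight weeks in both arms, and change taken from each arm's first section 5 questionnaire.

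- Test, week 1 to 8: 7T/8
- Control, week 4 to 8: 4T/8
- False gap in favour of test: 3T/8

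The planned effect is 75 − 66 = 9 points.

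| T (assumed) | False gap |
|---|---|
| −10 | −3.75 (against test) |
| 0 | 0 |
| 10 | 3.75 |
| 20 | 7.5 |

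The gap would equal the planned 9 points only at T = 9 × 8/3 = 24.

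For T = 10, take 120 per arm (240 in total, 1:1 allocation assumed), full retention and a within-person correlation of 0.5. The SD of change is 24 × √(2 × (1 − 0.5)) = 24, and the standard error is 24 × √(2/120) = 3.10. A two-sided 0.05 z-test then rejects about 23% of the time instead of 5%. At correlations of 0.3 and 0.7 the figures are about 18% and 35%.

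**3. What a baseline would add to a week-8 comparison**

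First, the plan's own figure. The standardised difference is 9/24 = 0.375. A two-sided 0.05 t-test with 120 per arm has power 0.825, consistent with the stated 0.8 for the combined analysis before dropout. With 77% retained, 120 × 0.77 = 92 per arm and power is 0.716.

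Adjusting for a baseline with correlation r to the outcome reduces the residual SD to 24 × √(1 − r²). The documents give no value of r, so a range is shown.

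| r (assumed) | Residual SD | Standardised difference | Power, 120 per arm | Power, 92 per arm |
|---|---|---|---|---|
| none | 24.0 | 0.375 | 0.825 | 0.716 |
| 0.3 | 22.9 | 0.393 | 0.858 | 0.756 |
| 0.5 | 20.8 | 0.433 | 0.916 | 0.832 |
| 0.7 | 17.1 | 0.525 | 0.982 | 0.943 |

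**The case against.** The best defence is that the only quantified drug-use measure in the plan is a level: percent days abstinent at week 8, the quantity used for the sample size. Both arms are assessed at week 8, and a comparison of levels between randomised arms needs no baseline to be valid. This stands, and it limits the point. It does not remove it, because section 6 lists changes, not levels, as primary.

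A reader might infer that the schedule favours the test arm by construction. The documents do not support that. Nowhere is change defined as last minus first questionnaire. The direction depends on abstinence rising in both arms, which the documents do not establish. Section 5 enrols people maintained on methadone, who may already be stable, and people moving from inpatient to outpatient care, whose abstinence could fall. If change ran from week 4 in both arms, the error would go the other way, because early program benefit would be lost.

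A reader might also infer that no baseline is collected. The questionnaires and the consent-form time table are cited as attachments and are not in the review copy, so either could contain one. The supportable statement is that the protocol text neither describes nor uses a baseline.

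Section 3's weekly questionnaire, if given to both arms, would supply a common week-1 value and remove the 3T/8 gap. That value would still be post-allocation, and the passage contradicts section 5 on who delivers questionnaires and, for control, how often. Last, ANOVA was chosen so that results can be compared with the earlier trials. That is a fair reason to report it, but not a reason to omit a baseline.

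**Conclusion.** The point holds as a gap in specification. The text describes no assessment before allocation, gives the arms different schedules, makes change primary without a reference time, and contradicts itself between sections 3 and 5 on questionnaire delivery and frequency.

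The bias is conditional. It arises if change is taken from each arm's first section 5 questionnaire and drug use has a trend common to both arms. Its size is then 3T/8 under linearity, for example 3.75 points at T = 10. T, its sign and linearity are assumptions, so this is not a forecast.

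The loss of precision applies even to the valid week-8 comparison. At assumed correlations of 0.3 to 0.7, adjustment would raise power from 0.825 to 0.86–0.98 with 120 per arm, and from 0.72 to 0.76–0.94 with 92 per arm. At the low end the gain is modest, and with 77% retained it would not restore 0.8. The change should be made; it is cheap, and the baseline has to be taken before treatment begins.

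**What to change.** **Section 5.** State that both arms complete the same questionnaire, covering use in the past 30 days, after consent and before the arm is revealed. Give both arms the same core assessment times (weeks 4 and 8) and the same recall window. Additional weekly contacts in the test arm can remain but should not feed the between-arm comparison.

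**Sections 3 and 5.** Reconcile who delivers the questionnaires and how often, by arm.

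**Section 6.** Make the drug-use analysis a comparison of week-8 percent days abstinent by analysis of covariance, adjusted for the baseline value. Define any change in drug use or health from that baseline in both arms. Report the unadjusted ANOVA alongside, for comparison with the earlier trials.

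**Cost.** One short questionnaire per participant at the existing meeting with the Research Assistant; eligibility already asks about the past thirty days. If the attachments show that a baseline is already collected, only the wording and the analysis change.

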A collaboration has now been formed between [name] and Drs [name] and [name] of the UPEI Centre for Health and Community Research (CHCR) that will bring CBT4CBT to Canada. While CBT4CBT has previously been tested in urban areas, there are many advantages to offering computer-based training to more rural populations (such as PEI). These more remote areas frequently suffer from a lack of services, as well as a lack of continuity with the services currently offered. CBT4CBT may very well provide that needed continuity to Addictions treatment and has also been shown to improve retention.

3. BACKGROUND, RATIONALE AND STATEMENT OF RESEARCH QUESTION(S):

CBT4CBT will be the first computer-based, cognitive behavioural therapy program for Addictions treatment to be offered in Canada. CBT4CBT has been rigorously tested in urban populations in the United States but this collaboration will be the first pilot trial in First Nation and other rural communities in Canada. Prince Edward Island has a self-proclaimed need for innovative new substance abuse treatments and CBT4CBT may provide the continuity and retention to traditional therapy programs that current available treatment options often lack. This study will allow CBT4CBT to be tested in several Prince Edward Island communities to gage its efficacy and effectiveness. The results and feedback received from the pilot study will allow the program to be adapted for Canadian populations in order to optimize its positive outcomes within Canada.

CBT4CBT has been tested in urban populations in the United States in three rigorous randomized clinical trials with great success. The nature of CBT4CBT suggests it would also be beneficial in rural and remote populations which are common across Canada. Computer based treatments are cost-effective and although their nature necessitates human participants they have minimal risk associated with them. As the first computer based training for Addictions in Canada this research project could have broad implications for treatment in Addictions across our country.

Analysis techniques will be based on those used in previous CBT4CBT trials conducted by our collaborator, [name].

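### Eight Research Assistant meetings in the test arm against two in control: a difference in retention or abstinence cannot be credited to CBT4CBT alone

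*Combined protocol and SAP*

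**What the plan says.** All of the schedule is in section 5 (Research Plan) of the combined protocol and SAP. Control participants receive the site's usual treatment and "will also meet with the Research Assistant during week 4 and week 8 to complete questionnaires". Test participants also receive usual treatment and "will also be asked to spend at least thirty minutes per week using the program", with use monitored. On meetings, the plan says: "The individuals in this arm of the trial will also meet with a Research Assistant once a week for eight weeks to complete questionnaires". Both arms are contacted again six months after the eight weeks.

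The same section gives the time asked of participants beyond usual treatment. For the test arm this is "approximately 45 minutes as a weekly average from participants in the test group"; the corresponding control figure is about 10 minutes. The section allows questionnaires to be completed online, and it makes their content the same in both arms apart from sections about CBT4CBT. It does not make their frequency the same. Participants are told their arm.

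Section 3 (Background), in its closing paragraph on outcomes, gives a different account: counsellors deliver a questionnaire every week to their patient in the trial, with no arm named. It also states that abstinence is self-reported. Section 6 (Analysis of Data) lists retention and change in drug use among the primary outcomes.

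The available text gives no reason for the different meeting schedules, no attention-matched control, and no way of handling the difference in the analysis.

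**The concern.** The design is meant to show what CBT4CBT adds to usual treatment. For that, the arms should be alike in everything else the study does to participants. They are not: on section 5's schedule the test arm has six more meetings with study staff and six more occasions of self-report. The meetings are described only as a means of completing questionnaires, not as part of CBT4CBT or of usual treatment.

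The outcomes at risk are primary ones. A standing weekly appointment might keep people in treatment, and repeated reporting of drug use might change either the use or the report. Section 3 states the hope that "CBT4CBT may provide the continuity and retention to traditional therapy programs that current available treatment options often lack", and regular staff contact could supply the same thing. The trial is open-label and abstinence is self-reported, so nothing in the measurement guards against this.

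Restricting the comparison to the shared time points (week 4, week 8, six months) does not remove the problem, because contact has already differed by then. At stake is what a positive result may be said to show: an effect of the program, or of the program together with weekly contact.

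**Working it through.** **Contact frequency (section 5).** Test: 1 meeting per week × 8 weeks = 8. Control: weeks 4 and 8 = 2. Difference 6, ratio 4 to 1.

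**Stated time (section 5).**
- Total beyond usual treatment over eight weeks: test 45 × 8 = 360 min; control 10 × 8 = 80 min.
- Program minimum in the test arm: 30 × 8 = 240 min.
- Non-program time: test 360 − 240 = 120 min; control 80 min.
- Excess: 120 − 80 = 40 min, or 40 / 8 = 5 min per week.

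With the 45-minute average taken as given, 40 minutes is an upper limit, since 30 minutes of program use is a minimum; part of it also goes on the added CBT4CBT sections. The imbalance is thus large in number and regularity of contacts and small in stated minutes.

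**What an unequal-contact effect would do to the test.** The plan has no figure on this to reproduce, and the documents give no contact effect. The calculation below is illustrative only.

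Inputs: SD 24 points and planning difference 75 − 66 = 9 points of days abstinent (section 6); 240 participants in the combined analysis (section 6), so 120 per arm, which matches 30 per group × 4 settings. Assumed: 1:1 allocation, two-sided 0.05 (the plan does not state sides), all participants analysed, true program effect zero, and a shift b due to contact alone.

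Standard error of the difference = 24 × √(2/120) = 3.10. The probability of a significant result is that of a two-sided t-test with 238 degrees of freedom and noncentrality b / 3.10:

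| Assumed shift b (points) | b / 3.10 | Probability of p < 0.05 |
|---|---|---|
| 0 | 0 | 0.050 |
| 1 | 0.32 | 0.062 |
| 2 | 0.65 | 0.099 |
| 3 | 0.97 | 0.161 |
| 5 | 1.61 | 0.362 |

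A shift of 2 points would be 2/9 = 22% of the planning difference. The table is symmetric: a shift of the same size against the test arm gives the same total probability, mostly in the other direction.

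For retention, take 77% in control (the average in section 6) and a two-proportion z-test with 120 per arm. Assumed test-arm values of 80%, 82% and 85% from contact alone give 0.09, 0.16 and 0.35.

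A larger sample does not help. With 220 per arm (the further 440 participants of section 4, if the schedule and 1:1 allocation carry over), the standard error is 24 × √(2/220) = 2.29, and shifts of 2 and 3 points give 0.14 and 0.26.

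**The case against.** The strongest case against runs as follows.

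- *The extra contact is trivial.* Five minutes a week of form-filling, possibly online, is unlikely to change drug use. The minutes are as stated and should temper any claim about size. But the text still schedules weekly meetings, and a fourfold difference in regularity is not measured in minutes. If online completion replaces the meetings, the difference in assessment frequency remains. The consent-form time table, which might settle this, is not available here.
- *Section 3 has weekly questionnaires for everyone.* If that sentence covers both arms, most of the imbalance in self-report goes. It names no arm and conflicts with section 5 on both who delivers the questionnaires and how often. Section 5 is specific to each arm, so it is the better guide, but the conflict needs resolving.
- *A package comparison is legitimate.* This stands. Section 3 sets a focus on feasibility, and section 5 says the design follows earlier US trials; whether those used this visit schedule cannot be seen here. Randomisation supports inference about the package as delivered.
- *The illustration proves nothing about this trial.* Also fair: any bias of the same size would give the same table.

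A reader might go further and infer three things that the documents do not support. The first is that no gain could be credited to CBT4CBT at all; the program is part of the package, so only sole credit is lost. The second is that the bias must favour the test arm; weekly questionnaires could also tire participants, or increase disclosure of use. The third is that the trial fails a stated aim of offering the program by itself as a low-cost option. Section 5 tests it on top of usual treatment, section 7 aims for it to become a standard option within treatment programs, and section 3 mentions cost-effectiveness only as background.

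**Conclusion.** The concern holds in a limited form. On section 5's schedule the arms differ by eight meetings to two as well as by CBT4CBT, and the plan neither explains nor handles this. A difference in retention or self-reported abstinence would estimate CBT4CBT plus weekly contact against usual care with two contacts. It would not isolate the program.

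How much this matters numerically is unknown. The plan's averages suggest a modest difference in time; the probabilities above rest wholly on assumed shifts and show only that a few points would be enough to mislead. The conclusion also depends on section 5, rather than section 3, describing what will be done. This is a weakness of interpretation that is cheap to remove, and does not invalidate the trial.

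**What to change.** 1. Reconcile the weekly counsellor questionnaire in section 3 with section 5: state who delivers questionnaires, in which arm and in which weeks.
2. In section 5, set one schedule for both arms: Research Assistant meetings at weeks 4 and 8 and the six-month follow-up contact, with the CBT4CBT sections completed by the test arm on those occasions. Program use is already monitored without meetings.
3. If weekly data are wanted, collect them with the same short online questionnaire, without a meeting, in both arms and on the same weeks.
4. If the schedules stay different, say in section 6 that conclusions apply to CBT4CBT together with weekly contact.

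Cost: revised wording and an ethics amendment, with no extra participants or staff; Research Assistant time falls under item 2. The downside is less frequent in-person feedback, which feeds a secondary outcome (section 7), and possibly slightly lower program use. Item 3 would instead add a little to the control arm's burden, above the stated 10-minute average.

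### The plan describes no stratification or blocking by site and names no site factor in its ANOVA, although usual care is defined by site and results are pooled over sites

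*Combined protocol and SAP*

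**What the plan says.** Section 5 (Research Plan) states "Participants will be randomized to either test or control groups". A Research Assistant is to "assign them a participant number generated using Randomizer.org", and of that number it says "This number will have been previously assigned to either test or control". That is the whole description of allocation. The ratio is not given; 1:1 is inferred from a single size quoted for each group.

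The same section defines the control as "treatment as usual (the conventional treatment offered at that site". Section 4 lists First Nation health centres, a transition unit, methadone clinics, two student services and a hospital on Prince Edward Island, plus one site each in New Brunswick and Ontario.

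The groups to be compared are populations: transitioning patients, youth, people on methadone, and indigenous individuals. A participant may belong to more than one. They "will be analyzed individually as well as collectively by compiling results from all sites".

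On size, section 4 says "A total of 240 Participants will be recruited during years 1-2 and an additional 440 participants will be recruited during years 3-4". Section 6 says "These values were used to calculate the sample size of 30 (for each group") and adds "The outcomes to be determined are identical in the four parallel trials to foster comparability across populations". The analysis in section 6 is one- and two-way ANOVA where appropriate, with no factor named beyond that.

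**The concern.** When the comparator is set locally and the sites serve very different people, mean abstinence can be expected to vary by site. If site plays no part in either the allocation or the model, two things follow:

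- Variation between sites is counted as error, so the standard error of the pooled treatment effect is larger than it need be.
- In a comparison of about 30 per arm, one arm can by chance draw more participants from a high-abstinence site, which shifts the estimate.

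The second matters most in the population subgroups, which are small and may span several sites. An imbalance in allocation cannot be undone after enrolment, although a site term can still adjust for it.

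**Working it through.** **Inputs.** From section 6: abstinent days 75% versus 66% (difference 9 points), SD 24, 30 per group for the initial subgroup analyses, 240 combined. Assumed, because the documents do not give them: equal sites (10 of 24 in the formulas below), between-site SD of 0, 8 or 12 points within a total SD of 24, two-sided tests, no attrition.

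**1. The plan's own figures.**
- Combined: SE = 24 × √(2/120) = 3.10; 9/3.10 = 2.905; power = Φ(2.905 − 1.96) = 0.828. This supports the stated 0.8 before attrition.
- Subgroup: 30 per group at the printed alpha of 0.5 gives 79.8% by two-sided t-test, matching the stated 0.8. At alpha 0.05 it gives 29.8%. The printed alpha is a separate matter; both values are carried below.

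**2. Do unequal arms matter?** Under simple randomisation of 60, a split of 25:35 or worse has probability 2 × P(Bin(60, 0.5) ≤ 25) = 24.5%. The cost in power (t-test) is small:

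| Split | alpha 0.05 | alpha 0.5 |
|---|---|---|
| 30:30 | 29.8% | 79.8% |
| 25:35 | 29.1% | 79.2% |

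**3. Pooled analysis with and without site.** With site-stratified allocation and a site term, the error SD is √(24² − τ²), where τ is the between-site SD, and SE = √(24² − τ²) × √(2/120).
- τ = 0: SE 3.10, power Φ(0.945) = 0.83.
- τ = 8: √512 = 22.63, SE 2.92, 9/2.92 = 3.08, power Φ(1.12) = 0.87.
- τ = 12: √432 = 20.78, SE 2.68, 9/2.68 = 3.35, power Φ(1.39) = 0.92.

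Simulations of 4,000 and 6,000 runs agree. The middle column has a site term but simple allocation:

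| Between-site SD | Simple, no site term | Simple + site term | Stratified + site term |
|---|---|---|---|
| 0 | 0.83 | not reported | 0.83-0.84 |
| 8 | 0.82-0.83 | 0.85 | 0.87 |
| 12 | 0.83-0.84 | 0.90-0.905 | 0.91-0.92 |

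The site term gives most of the gain. Stratification adds about 0.5 to 2 points on top. The formula agrees on that step: simple allocation keeps on average (24 − 1)/24 = 0.958 of the within-site information, so at τ = 8 the SE is 2.92/√0.958 = 2.98 and power is 0.85.

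**4. Chance site imbalance in one subgroup.** Assume a subgroup of 60 drawn from two sites of 30 whose mean abstinence differs by D points. With 30 per arm and no stratification, the number in the test arm from one site has SD √(30 × 0.25 × 30/59) = 1.95. The shift in the treatment difference then has SD 2 × 1.95/30 × D = 0.13 D. This gives 1.3 points at D = 10 and 2.6 at D = 20, against a target of 9. The SE of the comparison is 24 × √(2/30) = 6.20, so site contributes (1.3/6.20)² = 4% to (2.6/6.20)² = 18% of the error variance. Stratification or a site term would remove it.

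**The case against.** Four objections deserve an answer.

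- **Silence is not absence.** A pre-assigned list could be simple, balanced centrally, blocked, or held per site, and section 5 says the design mirrors earlier US trials whose allocation methods are not given. A reader might infer that the plan rules out blocking and stratification. The documents support only that none is described.
- **Uneven arms are nearly harmless.** A reader might infer that settings falling short of 30 per arm seriously weaken the trial. Step 2 shows they do not. Figures such as a 67.5% chance that at least one of four settings splits 25:35 or worse, or an 81% chance that at least one of ten sites splits 8:16 or worse, assume simple randomisation and equal, disjoint, independent groups. The documents state none of this, and the population groups can overlap. Those figures do not measure harm.
- **There is no bias.** Simple randomisation is unbiased over repeated trials, and its standard error already reflects chance imbalance. This stands; what is lost is precision.
- **Site effects are not documented.** The documents say usual care is site-specific but give no abstinence by site, and two-way ANOVA leaves room for a second factor. Both are true, so the gain is shown as a range that starts at zero. But no second factor is named, and leaving it open lets it be chosen after the data are seen.

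**Conclusion.** The point holds as one of efficiency and specification. Allocation by site is not described and site is not in the stated analysis, although the control condition depends on site. With the assumptions listed, doing both would raise pooled power by about 4 to 5 points at a between-site SD of 8 and about 8 points at 12, and would cost nothing material at 0. Adjustment accounts for most of this. In subgroups of about 60 the avoidable chance shift has an SD of 1.3 to 2.6 points if two sites differ by 10 to 20.

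The point does not show that the trial is invalid, that its estimates would be biased, or that unequal arms undermine the subgroup analyses. The 30 per group belongs to the initial 240; the same omission applies to the later 440. Attrition would lower all the power figures above.

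**What to change.** **Section 6.** Include site as a factor in the two-way ANOVA of the pooled data, and in any subgroup analysis that spans several sites. This matters more than the change to allocation.

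**Section 5.** Generate one 1:1 list per site in randomly varying blocks of 4 and 6, and keep the next assignment concealed until the participant is enrolled. Site is the right stratum because it is known at enrolment, is mutually exclusive and determines usual care. It will not guarantee 30 per arm in the overlapping population subgroups, and the text should not imply that it does. If a blocked or per-site list already exists, one sentence saying so settles this part.

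**Cost.** Minutes of list preparation before enrolment at each site, and one model term using a few degrees of freedom (nine with ten sites). Assignments become slightly more predictable within blocks, which varying block sizes and concealment limit.
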